2.1 Study Setting

The trial will be conducted at outpatient therapeutic program (OTP) centers in Gombe State, Nigeria, which are run out of government-run primary healthcare centers (PHC) that Taimaka partners with for their CMAM program. Taimaka's program uses these OTPs to run nutritional programs for children presenting with SAM. The PHCs are government-run, integrated health centers and are overseen by the Primary Healthcare Development Agency. Taimaka's program links these centers to secondary facilities for referrals in the case of complications. The secondary facilities function as inpatient treatment centers (ITPs) and are overseen by the Hospital Services Management Board and the Ministry of Health.

2.2 Recruitment and Eligibility Criteria

Recruitment

Taimaka-employed community mobilizers (CMs) screen children for SAM at least once a month in the villages within the catchment areas of the program PHCs. If they are screened positive for moderate acute malnutrition (MAM) or SAM, they are referred to an OTP center. CMs screen for MAM and SAM using a tape to measure mid-upper arm circumference (MUAC).

Each participating OTP center has nutrition staff (henceforth known as health agents) trained to enter data and conduct anthropometric measurements. All data is collected electronically on an ODK custom platform. The health agents at the OTP centers are trained regularly on malnutrition guidelines, data collection and anthropometric measurements

All children presenting to the OTP centers for malnutrition will be screened, and eligibility for enrollment in the trial will be determined by health agents trained for the study.

Eligibility criteria for enrollment sites

For Phase 1, the 3 Taimaka-run OTP centers in Gombe state that will be eligible for enrollment are located within 1) General Hospital Deba, 2) General Hospital Bajoga, and 3) General Hospital Billiri.

For Phase 2, the Taimaka-run OTP centers in Gombe state will be located in PHCs in wards in these local government areas (LGAs): Deba, Billiri, and Funakaye (Bajoga is a town within the Funakaye LGA).

Eligibility criteria for individuals

Eligible individuals are children aged 6-59 months with SAM who present to an eligible OTP center during the study period and meet all of the following criteria:

Inclusion criteria (all must be met):

- Age 6-59 months
- Weight-for-height z-score (WHZ) < -3 SD or mid-upper arm circumference (MUAC) < 115 mm
- Either (a) no oedema or (b) Nutritional edema Grade I and II
- Primary residence within catchment area of enrollment site
- Available for full 8-week study
- Sufficient appetite according to a feeding test with ready-to-use therapeutic food (RUTF)
- Appropriate written informed consent from at least one parent or guardian

Exclusion criteria (any excludes):

- Age < 6 months or > 59 months
- WHZ \geq -3 SD or MUAC \geq 115 mm
- Primary residence outside catchment area of enrollment site
- Not available for full 8-week study
- Presence of nutritional edema Grade III
- Admission to a nutritional program for the treatment of SAM in the 2 preceding weeks
- Antibiotic use in past 7 days
- Clinical complications requiring antibiotic treatment
- Clinical complications requiring inpatient treatment
- Congenital abnormality or chronic debilitating illness that would lead to predictable growth faltering or reduce likelihood of SAM treatment benefit (such as cerebral palsy, Down syndrome, congenital heart disease, cleft lip/palate, sickle cell disease etc)
- Allergy to macrolides/azalides
- Insufficient appetite according to a feeding test with ready-to-use therapeutic food (RUTF)
- Parent or guardian refuses to provide consent

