2.6 Participant Timeline

Figure 1. Participant Timeline and Flow

- Clinical examination outcomes (diagnoses, treatments)

Monthly:

- Anthropometry (Height, length)

Week 8:

- Malaria RDT

Week 12:

- Anthropometry (height, weight, MUAC)
- Vital Status

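### Section 2.2: the WHZ/MUAC exclusion line is not the complement of the inclusion line, so a child meeting only one criterion is both admitted and removed

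*Combined protocol and SAP*

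**What the plan says.** Section 2.2 sets eligibility by two lists. The first is headed "Inclusion criteria (all must be met" and its anthropometric line reads "Weight-for-height z-score (WHZ) < -3 SD or mid-upper arm circumference (MUAC) < 115 mm". The second is headed "Exclusion criteria (any excludes" and its anthropometric line reads "WHZ \geq -3 SD or MUAC \geq 115 mm". The same section makes site staff responsible for applying them: "eligibility for enrollment in the trial will be determined by health agents trained for the study".

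Three other places bear on the point.

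- Section 2.3 speaks of enrolling children who satisfy the inclusion criteria. It does not mention the exclusion list.
- The admission and discharge table in Section 2.5 gives low MUAC, bilateral oedema and low WHZ as separate admission rows. The text above it ties each child's recovery criterion to the criterion on which that child was admitted.
- The protocol update log, under 7 October 2022, records a clarification of the criteria in Sections 2.2 and 2.6. The conflict is in the current text all the same.

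**The concern.** The exclusion line appears meant to restate the inclusion line in the negative, but it keeps the wrong connective. A health agent who works from the inclusion list enrols a child with MUAC below 115 mm and WHZ at or above -3 SD. One who also applies the exclusion list turns the same child away. Each can claim to be following Section 2.2.

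Such a child is easy to envisage. Under Section 2.2 the community mobilizers screen on MUAC alone, so a child can be referred on MUAC and then prove to have WHZ at or above -3 SD at the centre. Eligibility is decided at three centres in Phase 1 and at health centres across three local government areas in Phase 2, so practice could differ between sites. A monitor could not say whether enrolling such a child, or refusing one, was the deviation.

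At stake are who is enrolled, how quickly the target of 600 is reached, and to whom the result applies.

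**Working it through.** No figure in the plan bears on this, so the check is one of logic.

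**Inputs (Section 2.2).** Let A = WHZ < -3 SD and B = MUAC < 115 mm.

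- Inclusion line: A or B.
- Exclusion line as written: (not A) or (not B), which equals not (A and B).
- Exact complement of the inclusion line: (not A) and (not B).

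| Child | Included? | Excluded as written? | Result | Excluded if the line used *and*? |
|---|---|---|---|---|
| A and B | yes | no | enrolled | no |
| A only | yes | yes | conflict | no |
| B only | yes | yes | conflict | no |
| neither | no | yes | out | yes |

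The inclusion line admits 3 of 4 combinations and the exclusion line removes 3 of 4. They overlap in 2, and 1 can be enrolled under the literal text.

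**The two possible repairs.**

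- *And* in the exclusion line: 0 conflicts, 3 of 4 combinations enrollable.
- *And* in the inclusion line, exclusion line unchanged: 0 conflicts, 1 of 4 enrollable.

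**Which reading was probably intended.** Each of the 7 inclusion lines has a counterpart in the exclusion list. Of the 6 other than WHZ/MUAC, 4 are exact complements (age, residence, availability, appetite) and 2 are close (oedema grade, consent). The age line, "Age < 6 months or > 59 months", uses *or* correctly because it negates a range. The appetite line, "Insufficient appetite according to a feeding test with ready-to-use therapeutic food (RUTF", is a plain negation of its partner. Only the WHZ/MUAC pair negates a disjunction, and there *or* has to become *and*. The separate admission rows in Section 2.5 point the same way. If every child had to meet both criteria, the rule that recovery follows the admitting criterion would no longer pick out one of the WHZ and MUAC rows.

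**Illustration of scale, on an assumption.** Let p be the share meeting both criteria among children who meet at least one, satisfy everything else and have consent. The documents do not give p. To enrol 600 (Section 9.1), the literal rule needs 600/p such children:

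- p = 0.25: 600/0.25 = 2,400
- p = 0.50: 600/0.50 = 1,200
- p = 0.75: 600/0.75 = 800

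The either-criterion rule needs 600. These numbers show only how the requirement varies with p. They do not estimate recruitment in this trial.

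**The case against.** The strongest reply is that there is no true contradiction. Exclusion lists exist to remove children whom the inclusion list lets in, and a child with recent antibiotic use is also included and then excluded. Applied in order, the two lists give one answer: enrol only if both criteria are met. That is right as formal logic. But the antibiotic exclusion adds a new condition, whereas this line acts on the same two measurements and cancels the alternative the inclusion line has just offered. A list that offers a choice and then withdraws it does not tell staff what was meant.

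A second reply is that intent can be recovered. Section 2.3 refers to the inclusion criteria alone, Section 2.5 lists separate admission routes, and nothing visible outside the exclusion line suggests that both criteria are required. This makes a slip likely and lowers the practical risk, but it does not correct the operative text. The Section 2.5 table describes the feeding programme, and a trial may enrol a subset of it. The table also has a row for oedema. A child admitted on oedema alone fails the WHZ/MUAC inclusion line under either repair, so the table cannot be read as the trial's eligibility rule.

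Third, the effect in practice is unknown. The content of "Figure 1. Participant Timeline and Flow" in Section 2.6 is mostly missing from the text available here, and the study forms in Appendix 2 were not available. The electronic form may already apply one reading. That stands, and it limits the finding to the wording of Section 2.2.

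**Conclusion.** The concern holds. As written, Section 2.2 both includes and excludes a child who meets exactly one of the two criteria (2 of 4 combinations). Followed literally, it restricts the trial to children who meet both. This rests on the text alone and needs no outside figure.

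The consequence is an ambiguous study population, with possible effects on recruitment and applicability. Eligibility is settled before allocation, so the comparison between arms is not biased. The number of children affected cannot be computed without the share meeting both criteria. The point should be fixed because it concerns a core entry criterion and the correction costs almost nothing.

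**What to change.** Make the two lines exact complements. If either criterion is meant to suffice, the exclusion line should read WHZ ≥ -3 SD *and* MUAC ≥ 115 mm. If both are meant to be required, change *or* to *and* in the inclusion line and leave the exclusion line alone. The choice is the sponsor's. Then check the Section 2.6 figure and the electronic eligibility form against the chosen rule.

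A minor point for the same edit: the closing sentence of Section 3.5 can be read as listing which oedema grades qualify. Taken literally, it shuts out children with no oedema, whom Section 2.2 admits. It should be reworded to agree with Section 2.2.

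The cost is one word in Section 2.2, one sentence in Section 3.5, and a check of the figure and form. The corrected text would go to the review boards and the DSMC, since Section 8 makes study protocols subject to their review. No extra children or procedures are needed.

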2.3 Randomization and Masking

Children meeting inclusion criteria will be enrolled by a local health agent after consent from guardian is obtained. At enrollment, children will be assigned a study identification number. Enrolled children will then undergo a baseline assessment. The baseline assessment includes data collection on demographics and socioeconomic status as well as anthropometric assessments. After completion of the baseline assessment, children will be randomized to receive either (1) a single dose of directly observed oral azithromycin plus a 5-day course of placebo or (2) a 5-day course of oral amoxicillin.

The randomization sequence will be generated by the UCSF investigators using R (R Foundation for Statistical Programming, Vienna, Austria). Children will be randomized in a 1:1

fashion to a single dose of azithromycin with short course of placebo or a short course of oral amoxicillin. The randomization sequence will be linked to the study identification numbers and kept separately so outcomes assessors are not aware of the treatment allocation. When a child has been enrolled and has completed the baseline assessments, a different health agent will determine the allocation and will administer study medication indicated as described in Section 4.

To keep the allocation concealed, only the study nurse administering treatment will have access to the randomization allocations. The study nurse will treat the child in a private room without the outcome assessor present. For each enrolled child, the treatment administered will be recorded on the mobile data collection app not accessible by the outcome assessor.

Given the nature of the intervention, the personnel administering treatment will not be masked to treatment assignment. Participants will be masked to treatment assignment, as parents of the children given azithromycin will receive a placebo syrup to give their child. Outcome assessors will be masked to treatment assignment; this will be accomplished by assigning one health agent to administer treatment and a separate masked health agent to perform outcome assessments, including anthropometry, and vital status updates.

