4.1 Study Medication Description

The azithromycin used in the trial will be suspension Azithromycin (Everdestiny) made by Everdestiny Pharmaceutical Limited.

The oral amoxicillin routinely used at each OTP for treatment of uncomplicated severe acute malnutrition, which is suspension Amoxicillin (Emzor) by Emzor pharmaceuticals limited, will be used for this trial.

The placebo used in this trial to mask participants in the azithromycin arm will be made by a local pharmacy.

All medications and placebo used in the trial will be placed in generic bottles at the local pharmacy to blind participants to the trial arm. The study nurse and investigators will be unblinded to the bottles

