4.2 Dosage Information

Azithromycin will be administered as a single dose, in oral suspension form for children. Dosing will follow the WHO recommendations for treatment of active trachoma: Single dose of 20mg/kg in children (up to the maximum adult dose of 1g).

The placebo given to individuals in the azithromycin arm will be instructed to administer the placebo at a volume equivalent to the amoxicillin dose.

Individuals who are allergic to macrolides/azalides will not be treated.

Oral amoxicillin will be administered for 5 days. The first dose will be administered by the health agent, who will teach the caregiver how to administer the medication at home. The remaining doses will be administered by the caregiver.

Amoxicillin will be administered at a dose of 40mg/kg twice per day for 5 days.

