9. STATISTICAL METHODS

9.1 Sample Size and Power

Specific Aim 1 We assume that inclusion of 600 children (300 randomized to each arm) will provide 80% power to detect a 15% increase in weight gain (g/kg/day) in children receiving azithromycin compared to children receiving amoxicillin at an alpha of 0.05. Assumptions for this calculation were based on the pattern of weight gain reported in a trial of routine amoxicillin for uncomplicated SAM in Burkina Faso comparing children receiving azithromycin to amoxicillin over time.¹¹ We assumed an average weight gain of 2.6 g/kg/day over 8 weeks in the amoxicillin arm, with a standard deviation of 1.7 g/kg/day, and loss to follow-up of 10%. A 16% increase corresponds to a mean difference in weight gain of 0.4 g/kg/day, or an average weight gain of 3.0 g/kg/day in the azithromycin arm.

This calculation was performed in Stata using the following command:

```
power twomeans 2.6, sd(1.7) alpha(0.05) power(0.8) n(540)
```

Specific Aim 2. Inclusion of 600 children (300 randomized to each arm) will provide 80% power to detect a 12 percentage point difference in the proportion of children achieving nutritional recovery in the azithromycin arm compared to the amoxicillin arm. Assumptions for this calculation were based on nutritional recovery reported in the amoxicillin arm of a trial of routine amoxicillin compared to azithromycin for uncomplicated SAM in Burkina Faso.¹¹ We assumed that 36% of children in the oral amoxicillin arm would achieve nutritional recovery and a loss to follow-up of 10%.

This calculation was performed in Stata using the following command:

```
power twoproportions 0.36, alpha(0.05) power(0.8) n(540)
```

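### Allergy exclusion and dosing rule cover azithromycin's class only, so a child with known penicillin allergy can be randomised to amoxicillin

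*Combined protocol and SAP*

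**What the plan says.** Section 2.3 allocates children 1:1, after eligibility and baseline assessment, to "1) a single dose of directly observed oral azithromycin plus a 5-day course of placebo or (2) a 5-day course of oral amoxicillin".

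Allergy appears in two places. The exclusion list in Section 2.2 contains "Allergy to macrolides/azalides". Section 4.2 adds a rule at dosing: "Individuals who are allergic to macrolides/azalides will not be treated". Both concern the class to which azithromycin belongs.

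For the comparator, Section 4.2 states: "Amoxicillin will be administered at a dose of 40mg/kg twice per day for 5 days". The health agent gives the first dose and teaches the caregiver; then "The remaining doses will be administered by the caregiver". Section 4.1 describes the product as "The oral amoxicillin routinely used at each OTP for treatment of uncomplicated severe acute malnutrition". Section 9.1 plans for "inclusion of 600 children (300 randomized to each arm").

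The other antibiotic-related exclusions in Section 2.2 are recent antibiotic use and complications that need antibiotics. Neither concerns allergy.

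**The concern.** In a randomised comparison of two active drugs, a child should be enrolled only if either drug could be given safely, because eligibility is settled before the allocation is known. The protocol treats drug allergy as needing an explicit rule and states one twice, but for one arm only. No reason is given for leaving out the other.

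Followed literally, the criteria admit a child whose caregiver already knows of an amoxicillin or penicillin allergy, and neither section tells staff to withhold the drug. What is at stake is an avoidable and possibly serious reaction in a severely malnourished child.

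There is a smaller trial-conduct issue. If the nurse learned of the allergy and withheld amoxicillin on clinical judgement, this would happen after randomisation and in one arm only, and the available text does not say what the child should receive instead.

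**Working it through.** **Text check.** The two randomised drugs set against the allergy provisions:

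| | Azithromycin | Amoxicillin |
|---|---|---|
| Excluded for known allergy (Section 2.2) | yes | no |
| Withheld for known allergy (Section 4.2) | yes | no |
| Planned number assigned (Section 9.1) | 300 | 300 |

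No other available section mentions allergy to amoxicillin, penicillins or beta-lactams as an exclusion, a screening question or a dosing rule. The finding rests on this comparison; the figures below only give its scale.

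**Design figures in Section 9.1.** Inputs: SD 1.7 g/kg/day, amoxicillin mean 2.6 g/kg/day, two-sided alpha 0.05, power 80%, 10% loss to follow-up.
- Enrolment: 540 / (1 − 0.10) = 600, as stated.
- Detectable difference with 270 analysed per arm: (1.960 + 0.842) × 1.7 × √(2/270) = 0.41 g/kg/day. 0.41 / 2.6 = 15.8%, consistent with the 16% and 0.4 g/kg/day stated.

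The proposed change alters none of these.

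**Exposure.** 2 doses per day × 5 days = 10 doses. The health agent gives 1 and the caregiver gives 9, so 9/10 = 90% are given at home.

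**Number of children.** The documents give no allergy rate, so the caregiver-known rate p is assumed to lie between 0.1% and 2%.

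| Assumed p | Expected in amoxicillin arm (300 × p) | Chance of at least one, 1 − (1 − p)^300 | Excluded by the fix (600 × p) |
|---|---|---|---|
| 0.1% | 0.3 | 26% | 0.6 |
| 2% | 6 | 99.8% | 12 |

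**Effect on the primary estimate.** Suppose 2% of the amoxicillin arm did not receive the drug because of allergy, and each such child's weight gain changed by the full target difference of 0.4 g/kg/day. Both are assumptions chosen to be generous.
- Shift in the arm mean: 0.02 × 0.4 = 0.008 g/kg/day.
- Standard error of the difference: 1.7 × √(2/270) = 0.146 g/kg/day.
- Ratio: 0.008 / 0.146 = 0.055, about 5% of one standard error.

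This bounds the disturbance from withheld drug. It does not measure harm to a child who is given the drug.

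**The case against.** The strongest reply is that the trial adds no amoxicillin exposure. The drug is routine at these centers (Section 4.1), so these children would be expected to receive it anyway, and randomisation spares half of them. That may be why only the non-routine drug has an allergy criterion. This stands as a reason to regard the added risk as small. It does not justify leaving the criterion out, since routine use does not make the drug safe for an allergic child. Masking also weakens an informal safeguard: medicines go into generic bottles (Section 4.1) and the azithromycin arm receives a placebo syrup (Section 2.3), so a caregiver who knows of an allergy is not meant to know whether the home bottle contains amoxicillin.

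Second, the consent documents, study forms and standard medical protocol (Appendices 1, 2 and 4) and part of the Section 2.6 figure were not available. The update log records that eligibility was clarified in Sections 2.2 and 2.6, so the figure may restate the criteria. An allergy check could exist in any of these places. This stands as a limit: whether children go unchecked in practice cannot be established. If a check exists, the children are protected and what remains is a mismatch with Sections 2.2 and 4.2, which would still need correcting.

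Third, other safeguards exist. The person giving treatment is unmasked and gives the first dose, consent invites questions (Section 7.2), and adverse events, including skin rash, are asked about at follow-up visits (Section 5.1). These reduce the risk, and the supervised first dose limits what the 90% home-dosing figure can show. None of them requires anyone to ask about penicillin allergy, and adverse-event reporting acts only after exposure.

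Finally, the counts are an assumed rate multiplied out, and at the low end fewer than one child is expected. That is correct; the case does not depend on them.

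**Conclusion.** The concern holds. Sections 2.2 and 4.2 protect against allergy to one of the two randomised drugs and are silent on the other, so a child with known amoxicillin or penicillin allergy who meets the remaining criteria is eligible and can be assigned amoxicillin.

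The number affected is unknown: 0.3 to 6 of 300 under the assumed 0.1% to 2%. The consequence for the primary comparison is negligible. Confidence is high that the two sections omit the check, and lower on what happens at the sites, because the appendices and the full figure could not be read. The protocol should be corrected because the possible harm is serious and foreseeable, and the correction costs very little.

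**What to change.** Add known allergy to amoxicillin, penicillins or other beta-lactams to the exclusion criteria in Section 2.2, and extend the withholding rule in Section 4.2 to the same allergies. Ask every caregiver about both drug classes before randomisation, and apply the exclusion before the arm is known, so that the two arms remain comparable and no child needs an improvised substitute after allocation. Align the Section 2.6 figure and the screening form with the revised wording.

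The cost is one screening question and one line in each of the two sections. Under the assumed rates, about 0.6 to 12 of 600 otherwise eligible children would be excluded and replaced. The sample size and the analysis do not change.
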